5.1 Available sets for analysis

See also the Data Management Plan of the FAST 1 trial.

There are 2 data sources for this trial.

Revision	D02	Document number:	SAP
		Document title:	FAST-1
		Status:	APPROVED
		TPL 013.D02	This document is uncontrolled when printed

- Electronic data management system:
 - CRF
 - Study visits
- Artificial Pancreas

5.1.1 CRF Dataset

The CRF data will be collected with an eCRF implemented in *MyResearchManager*. The following data will be collected with the CRF:

- In- and exclusion criteria;
- Gold/Clarke questionnaire;
- Date of informed consent;
- Demography;
- Weight, length, HbA1c;
- Medical history;
- Randomization results;
- Visits information (including telephone contact, decided 'actions' and rationale);
- Concomitant medication;
- Adverse events;
- Device deficiencies;
- Adjustment of AP settings;
- End of study.

5.1.2 Artificial Pancreas dataset

The AP sends data to the AP Portal system every 10 minutes. The following data will be collected in the AP Portal system:

- AP, transmitters and mobile access point identification;
- Sensor glucose concentration;
- Sensor glucose slope;
- Sensor state;
- Insulin and glucagon administrations;
- Physical activity parameter measured by accelerometers;
- Control algorithm state;
- Events registered by the AP (e.g., low and high glucose alarm, calibrations, infusion set occlusion and replacements, sensor replacements).

5.2 Statistical analysis program

Python will be used for statistical analysis. Preparation of the dataset before statistical analysis will be done in Python as well. For a list of the used scripts, functions, as well as the version numbers of the used libraries refer to the Data Analysis Plan.

Revision	D02	Document number:	SAP
	Document title:	FAST-1	
	Status:	APPROVED	
	TPL 013.D02	This document is uncontrolled when printed	

5.3 Standard analysis

The distribution of each parameter (primary, secondary and other study parameters) will be assessed with a histogram and/or q-q plot. For the parameters that are being compared with dependent/paired tests, the distribution of the difference between the groups will be assessed. Based on these assessments, the decision for using data transformations and parametric or nonparametric descriptive analysis and statistical testing will be made for each (group of) parameter(s).

Subsequently, carry-over and period effects will be assessed because of the cross-over design of the study. For each parameter that will be compared between open loop and closed loop, the two randomization groups are first compared using two unpaired t-tests or Mann-Whitney U-tests:

- Sum of open loop and closed loop result (carry-over);
- Difference between the open loop and closed loop result (period).

If a significant difference is found in one of these tests, a carry-over/period effect is present. In that case, the results for that parameter of the second study period cannot be used for the analysis (to estimate the treatment effect) and paired testing will not be possible.

For all statistical tests described in this chapter, a p-value ≤ 0.05 is defined to indicate statistical significance. Descriptive analyses will be performed on the subjects presented in 5.3.3.

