4.4 Sample size calculation

It is hypothesized that the time above range is reduced in subjects using Lyumjev compared to Humalog. To detect a 3,125% (45 min per day – 15 min per meal) improvement in time spent in hyperglycemia (>10 mmol/l) with a power of 0.90 and alpha of 0.05, 10 subjects are required. To account for drop out of subjects, the sample size will be increased with 2 patients. The sample size calculation has been performed with the program G*Power 3.1.9.4. The percentage time above target range and corresponding standard deviations are based on data from the APPEL 5 study.

The following data were used to calculate sample size:

T-Test: Difference between two dependent means (matched pairs)

Alpha = 0.05

Power = 0.90

Mean 1 = 12.8

Mean 2 = 9.675

SD of mean 1 = 3.3

SD of mean 2 = 3.3

Correlation = 0.70

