10. STATISTICAL ANALYSIS

A general description of the statistical methods to be used is given in this chapter, specific details will be provided in the Statistical Analysis Plan. The Statistical Analysis Plan will be prepared before inclusion of the first patient. Deviations from this plan should be reported in the clinical investigation report with a clear statement that this decision was made after preliminary data evaluation and thus post-hoc.

All subjects that completed both study periods will be included in the analysis. Withdrawals will be included in the analysis for adverse events and device deficiencies in order to have an adequate amount of data for analysis. Furthermore, the data collected until their withdrawal will be included in the analysis as well. Carry-over and period effects will be assessed for all parameters.

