10.1 Primary study parameter

The proportion of time above range (>10.0 mmol/l) will be compared between Lyumjev insulin and Humalog insulin using a dependent t-test or Wilcoxon signed rank test for paired measurements (significance level of 0.05).

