5.3.1 Primary study parameter

The primary objective is to determine the efficacy of Lyumjev in the AP. The main parameter to express efficacy is the time above range (>10 mmol/l). It is hypothesized that the time above range is lower using Lyumjev compared to the standard use of care: Humalog by a margin of 3.125%. The proportion of time spent above the target range will be compared between the two types of insulin using a dependent t-test or Wilcoxon signed rank test for paired measurements.

$$H_0: (\mu_{\text{Lyumjev}} - \mu_{\text{Humalog}}) \geq -3.125\%$$

$$H_1: (\mu_{\text{Lyumjev}} - \mu_{\text{Humalog}}) < -3.125\%$$

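### SAP 5.3 discards period 2 and bars the paired test when a carry-over or period pre-test has p ≤ 0.05, and names neither a replacement test nor a period-adjusted analysis

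*SAP*

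**What the plan says.** Protocol 10 says only this: "Carry-over and period effects will be assessed for all parameters". It attaches no consequence.

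SAP 5.3 adds one. The two sequences are compared with unpaired t-tests or Mann-Whitney tests on the sum and on the difference of each patient's two results. Either test alone is the trigger: "If a significant difference is found in one of these tests, a carry-over/period effect is present". Two consequences follow. Period 2 is lost: "the results for that parameter of the second study period cannot be used for the analysis (to estimate the treatment effect"). The planned test is lost with it: "and paired testing will not be possible". The threshold is p ≤ 0.05, and the rule is applied separately to each parameter, the primary included.

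The only treatment tests named for the primary parameter are paired. Protocol 10.1 compares the insulins "using a dependent t-test or Wilcoxon signed rank test for paired measurements (significance level of 0.05"). SAP 5.3.1 names the same two tests: "The proportion of time spent above the target range will be compared between the two types of insulin using a dependent t-test or Wilcoxon". The sample size in protocol 4.4 rests on "T-Test: Difference between two dependent means (matched pairs"). Neither document contains a period term, a mixed model or a test for period-1 data alone.

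The rule is introduced with the words "For each parameter that will be compared between open loop and closed loop". Those are not the arms of this trial, so it has to be read as Lyumjev and Humalog.

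**The concern.** The rule makes the primary analysis depend on two preliminary tests. When either is significant, the only named test is withdrawn and nothing is put in its place. Three faults follow.

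- A pure period effect triggers the loss of half the data, although a two-sequence design exists so that a period effect can be separated from the treatment effect.
- If the intended fallback is the comparison of period-1 results between sequences (implied but not written), that comparison is strongly correlated with the sum pre-test. Choosing it because the sum test was significant raises the type I error.
- The sum test has little power at this sample size, so passing it says little about carry-over.

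At stake are the power of the primary comparison, its error rate under one reading, and a defined analysis once the rule fires.

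**Working it through.** **Inputs.** Protocol 4.4 and SAP 3 give SD 3.3 in both conditions, correlation 0.70, means 12.8 and 9.675 (difference 3.125 points), alpha 0.05 and power 0.90. Allocation is equal (SAP 4), so 12 patients are taken as 6+6. The documents give no period or carry-over size; the values below are an assumed range.

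**The plan's own figure.** SD of differences = √(2 × 3.3² × (1 − 0.70)) = 2.556, and 3.125/2.556 = 1.223. A two-sided paired t-test against zero has power 89.3% at n = 9 and 92.9% at n = 10, so the stated 10 is reproduced. A one-sided test would already reach 92.7% at n = 8. The two-sided zero null is therefore the one behind the sample size, and it is used below unless stated.

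**Standard errors at 6+6.**
- Paired or period-adjusted treatment estimate: 2.556/√12 = 0.74 points.
- Period-1 comparison: 3.3 × √(1/6 + 1/6) = 1.91 points, 2.6 times as large. Its power at 3.125 points is 32%.
- Period pre-test: a period effect π shifts the contrast by 2π, with SE 2.556 × √(1/3) = 1.48.
- Sum pre-test: SD of the sum = √(2 × 3.3² × 1.70) = 6.085, SE 6.085 × √(1/3) = 3.51.

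**How often the rule fires with neither effect present.** 1 − 0.95² = 9.75% per parameter.

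**Power at 3.125 points, no carry-over** (simulated, normal data, 400,000 trials per setting):

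| Period effect (points) | Rule fires | Rule, assumed period-1 t-test | Rule, no test once it fires | Period-adjusted |
|---|---|---|---|---|
| 0 | 10% | 92% | 88% | 97% |
| 1 | 27% | 80% | 70% | 97% |
| 2 | 70% | 51% | 28% | 97% |
| 3 | 96% | 34% | 4% | 97% |

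Period-adjusted means the two-sample t-test of within-patient period differences between sequences.

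**Type I error, no period or carry-over effect.** With the assumed fallback it is 7.7% two-sided and 6.7% one-sided. The sum half of the rule alone gives 7.8%, the period half alone 5.1%. The cause is the correlation between a patient's sum and period-1 value, √((1 + 0.70)/2) = 0.92: given a significant sum test, the period-1 test is falsely positive in about 60% of trials. If no test follows, type I error is 4.5%. The adjusted analysis holds 5.0%.

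**Real carry-over λ in one sequence, no insulin difference.** Carry-over shifts the sum and the difference contrasts by the same λ, but their standard errors are 3.51 and 1.48. At 3.125 points that is 0.89 against 2.12 standard errors, so the difference test is the more sensitive of the two. It also biases the adjusted and paired estimates by λ/2.

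| Carry-over (points) | Sum test fires | Difference test fires | SAP rule rejects, assumed fallback | Adjusted rejects |
|---|---|---|---|---|
| 1 | 6% | 9% | 11% | 9% |
| 2 | 8% | 23% | 18% | 23% |
| 3.125 | 13% | 48% | 21–22% | 48% |

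The order reverses at about 1.5 points two-sided (adjusted 15% v rule 14%). One-sided, with Humalog values raised, it has already reversed at about 1 point (16% v 15%). At 3.125 points the plain paired t-test rejects in 35%. Only the period-1 comparison holds 5%.

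**The case against.** The strongest objection is that the rule gives some protection where it matters. Because the difference pre-test reacts to real carry-over, it supplies most of the rule's defence against it, and the proposed adjusted analysis does worse than both the rule and the plain paired test at 3.125 points. This stands. A reader might infer that the period half of the rule only loses power, or that adjustment is better throughout; both are true only without carry-over. It does not rescue the rule, which still rejects in 21–22% there.

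Second, the rule has no live consequence. Every parameter that 5.3.1 and 5.3.2 test is a sensor-glucose measure, and Deviation 3 excludes those data for the Lyumjev-Humalog sequence. This also stands as a limit on practical weight. A reader might infer that the rule distorted the reported result. The documents do not support that: with one sequence neither pre-test can be computed. Nor would adjustment repair the excluded data, since Deviation 3 records that the retained settings affected glucose regulation after the switch back to Humalog.

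Third, the figures rest on assumptions. No period effect is documented, the first five days of each period are excluded, and patients have used the system for at least a month. At 0 to 0.5 points the loss is from 97% to 92% or 89%. The type I inflation needs the unnamed fallback, so the documents do not show that the SAP as written inflates it. SAP 5.2 refers scripts to a Data Analysis Plan that is not available here, so the absence of a replacement test is established for these two documents only.

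Fourth, SAP 5.3.1 sets a one-sided null at −3.125%. Power at a true reduction of 3.125 points equals alpha there under any valid test, so the power figures above do not apply to that null. They fit the sample size calculation and protocol 10.1.

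**Conclusion.** The concern holds as a fault in the plan that should be fixed. The rule discards data for a period effect that one model term would remove, withdraws the only named primary test, and leaves the next step undefined. Without carry-over, the power cost is about 5 points with no period effect and 17, 46 and 63 points for period effects of 1, 2 and 3 points (97% less 92%, 80%, 51% and 34%); it is larger if no test follows. The type I error of 7.7% two-sided is conditional on the assumed period-1 fallback.

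These figures assume normal data, the plan's SD and correlation, 6+6 patients and a two-sided zero null. The case for adjustment is not unconditional: under a real carry-over of about 1.5 points or more (two-sided) it rejects falsely more often than the rule.

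For the reported glucose data, the relevant fact is a different one. With seven patients in one sequence, the assessment promised in protocol 10 could not be done and insulin is fully confounded with period. Section 8.1 does not say so.

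**What to change.** 1. Delete the pre-test and discard rule from SAP 5.3.
2. For any analysis with both sequences, use the period-adjusted crossover analysis: insulin and period fixed with patient random, or the two-sample t-test of within-patient period differences between sequences, with a Mann-Whitney test of those differences as the rank version.
3. Report period and carry-over estimates with confidence intervals, descriptively.
4. State that adjustment does not remove a real carry-over, and give the downside (48% v 21–22% false rejection at 3.125 points). Where carry-over is known from the conduct record, report the randomised period-1 comparison as a sensitivity analysis. It holds 5% but is imprecise: at 5 v 7 its SE is 3.3 × √(1/5 + 1/7) = 1.93, its 95% half-width about 4.3 points, and its power 31%.
5. In 8.1, state that for the retained data (n = 7, one sequence) carry-over and period effects could not be assessed and insulin and period are fully confounded. Qualify the conclusion accordingly.
6. Replace the open-loop and closed-loop wording with Lyumjev and Humalog, and log all changes as post-hoc, since revision D02 postdates the analysis decisions of May 2023.

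The cost is SAP wording, a few lines of code and one degree of freedom: power at 6+6 with no period effect goes from 97.0% (paired) to 96.7%. The rank version costs more in small samples. At 5+5 it has 84% power, against 88% for the rank form of the SAP rule with no period effect and 86% at 0.5 points; it is ahead from 1 point (84% v 79%). Steps 1 to 3 correct the plan; only step 5 bears on the reported result.

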5.3.1 Primary study parameter

The primary objective is to determine the efficacy of Lyumjev in the AP. The main parameter to express efficacy is the time above range (>10 mmol/l). It is hypothesized that the time above range is lower using Lyumjev compared to the standard use of care: Humalog by a margin of 3.125%. The proportion of time spent above the target range will be compared between the two types of insulin using a dependent t-test or Wilcoxon signed rank test for paired measurements.

$$H_0: (\mu_{\text{Lyumjev}} - \mu_{\text{Humalog}}) \geq -3.125\%$$

$$H_1: (\mu_{\text{Lyumjev}} - \mu_{\text{Humalog}}) < -3.125\%$$

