2. OBJECTIVES

Primary Objective:

The primary objective is to determine the efficacy of Lyumjev in the AP. Main parameter to express efficacy is the time above range (>10 mmol/l). It is hypothesized that the time above range is lower using Lyumjev compared to the standard use of care: Humalog.

Secondary Objectives:

Secondary objectives are:

- to assess safety parameters;
- to assess differences in pharmacodynamics between Lyumjev and Humalog;
- to assess differences in AP-related outcomes between Lyumjev and Humalog.

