Revision	D02	Document number:	SAP
	Document title:	FAST-1	
	Status:	APPROVED ON JULY 1, 2025	
	TPL 013.D02	This document is uncontrolled when printed	

Fully Automated glycemic control with ultrarapid insulin in a bihormonal closed loop System in patients with Type 1 diabetes (FAST 1)

Statistical Analysis Plan

Short title	FAST 1
Protocol ID	NL79588.091.22
(Coordinating) Principal Investigator	[name]
Responsible for data management	[name]
Based on protocol version	1.2 (dd 16-06-2022)

Revision	D02	Document number:	SAP
		Document title:	FAST-1
		Status:	APPROVED
		TPL 013.D02	This document is uncontrolled when printed

1 Content

2 Scope.....	3
3 Sample size.....	3
4 Randomization and blinding procedure	3
5 Statistical analysis	3
5.1 Available sets for analysis.....	3
5.1.1 CRF Dataset	4
5.1.2 Artificial Pancreas dataset.....	4
5.2 Statistical analysis program	4
5.3 Standard analysis.....	5
5.3.1 Primary study parameter	5
5.3.2 Secondary study parameters	5
6 Missing data.....	6
7 Interim analysis types	7
8 SAP deviations.....	7
8.1 Description of the deviations from the SAP	7
8.2 Signatures of the people involved in the decisions:.....	8
9 Revision History	9

Revision	D02	Document number:	SAP
		Document title:	FAST-1
		Status:	APPROVED
		TPL 013.D02	This document is uncontrolled when printed

2 Scope

This statistical analysis plan (SAP) applies to the main study of the FAST 1 trial and is developed for the statistical analysis performed by Inreda Diabetic B.V.

3 Sample size

It is hypothesized that the time above range is reduced in subjects using the artificial pancreas (AP) in combination with Lyumjev compared to Humalog. To detect a 3,125% (45 min per day – 15 min per meal) improvement in time spent in hyperglycemia (>10 mmol/l) with a power of 0.90 and alpha of 0.05, 10 subjects are required. To account for drop out of subjects, the sample size will be increased with 2 patients. The sample size calculation has been performed with the program G*Power 3.1.9.4. The percentage time above target range and corresponding standard deviations (SDs) are based on data from the APPEL 5 study.

The following data were used to calculate sample size:

- T-Test: Difference between two dependent means (matched pairs)
- Alpha = 0.05
- Power = 0.90
- Mean 1 = 12.8
- Mean 2 = 9.675
- SD of mean 1 = 3.3
- SD of mean 2 = 3.3
- Correlation = 0.70

4 Randomization and blinding procedure

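### SAP 5.3.1 puts the 3.125-point planning effect on the boundary of the primary null, so the stated 0.90 power does not describe the written test

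*SAP*

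**What the plan says.** **Sizing.** Protocol 4.4 and SAP 3 carry the same calculation: a matched-pairs t-test with means 12.8 and 9.675, both SDs 3.3, correlation 0.70, alpha 0.05 and power 0.90. The difference between the means, 3.125 points (45 minutes a day), is the improvement to detect, and "with a power of 0.90 and alpha of 0.05, 10 subjects are required". Two more were added for dropout. The inputs contain no margin and do not state one- or two-sided.

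**Primary hypothesis in the SAP.** SAP 5.3.1 says time above range is expected to be lower "compared to the standard use of care: Humalog by a margin of 3.125" percent. The null is "H_0: (\mu_{\text{Lyumjev}} - \mu_{\text{Humalog}}) \geq -3.125" percent, and the alternative is a difference below that value. A paired t-test or a Wilcoxon signed rank test may be used. SAP 5.3.1 does not state the sides, whereas SAP 5.3.2 calls each listed secondary comparison one-tailed. SAP 5.3 adds: "For all statistical tests described in this chapter, a p-value ≤ 0.05 is defined to indicate statistical significance".

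**Protocol.** Section 2 reads "It is hypothesized that the time above range is lower using Lyumjev compared to the standard use of care: Humalog", and section 10.1 reads "The proportion of time above range (>10.0 mmol/l) will be compared between Lyumjev insulin and Humalog insulin using a dependent t-test" or its Wilcoxon counterpart. Neither gives a margin. Section 10 leaves specific details to the SAP.

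**Later record.** SAP 8.1 logs three deviations, none of which concerns the null. The third limits the closed-loop glucose data to the 7 participants of the Humalog-Lyumjev sequence.

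**The concern.** A sample size calculation gives power at an alternative, measured from the null value. If the planning effect is itself the null value, the distance is zero and more patients do not help. As written, a drug that did exactly what the sponsor planned for would almost always fail to reject the primary null.

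Two things are at stake. First, a reader who sees 0.90 power may take a failure to reject the written null as evidence against a 3.125-point benefit, which it would not be. Secondly, the documents leave two definitions of primary success, one much easier to meet than the other. Unless the choice and its date are on record, a reader cannot tell whether it was made before or after the data were seen.

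**Working it through.** **Inputs** (Protocol 4.4, SAP 3): means 12.8 and 9.675, SD 3.3 in each condition, correlation 0.70, alpha 0.05, power 0.90.

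**1. Effect size.** Difference = 12.8 - 9.675 = 3.125 points (45/1440 = 3.125%). SD of the paired differences = 3.3 × √(2 × (1 - 0.70)) = 2.556. Standardised effect = 3.125/2.556 = 1.2225.

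**2. Reproducing the plan's figure.** Power comes from the noncentral t distribution with n - 1 degrees of freedom and noncentrality 1.2225 × √n (3.866 at n = 10), against a null of zero:

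| n | two-sided 0.05 | one-sided 0.05 |
|---|---|---|
| 7 | 0.769 | 0.885 |
| 8 | 0.841 | 0.927 |
| 9 | 0.893 | 0.955 |
| 10 | 0.929 | 0.972 |
| 12 | 0.970 | 0.990 |

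The smallest n reaching 0.90 is 10 two-sided and 8 one-sided. The stated 10 therefore fits a two-sided test of zero difference. A two-sided exact Wilcoxon test also needs 10 (simulated power about 0.92; about 0.85 at n = 9), so the match does not single out the t-test.

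**3. Power against the written null.** Noncentrality becomes (true reduction - 3.125)/2.556 × √n. At a true reduction of 3.125 it is 0 for every n, so power equals the level of the test: 5% for a one-sided t-test at 0.05, or 2.5% in the favourable direction with a two-sided p-value. An exact one-sided Wilcoxon test attains at most 4.2% (n = 10) or 3.9% (n = 7).

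**4. True reduction needed for 90% power against the written null** (t-test):

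| n | one-sided 0.05 | two-sided p-value |
|---|---|---|
| 7 | 6.34 | 6.91 |
| 10 | 5.69 | 6.08 |
| 12 | 5.43 | 5.76 |

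For scale, 5.69 points is 0.0569 × 1440 = 82 minutes a day and 5.69/12.8 = 44% of the assumed Humalog mean. The correlation matters: from 0.5 to 0.8, the one-sided figure runs from 6.44 down to 5.22 at n = 10 and from 7.28 down to 5.75 at n = 7.

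**5. Where the two tests part.** If the observed SD of differences is 2.556, the standard error is 0.808 (n = 10) or 0.966 (n = 7). The observed mean reduction must exceed:

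- zero null, two-sided: 2.262 × 0.808 = 1.83 (n = 10); 2.447 × 0.966 = 2.36 (n = 7);
- written null, one-sided: 3.125 + 1.833 × 0.808 = 4.61 (n = 10); 3.125 + 1.943 × 0.966 = 5.00 (n = 7).

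Reductions between those limits pass the first test and fail the second. At a true reduction of 3.125, 400,000 simulated trials per sample size put this at about 88% (n = 10) and 72% (n = 7). These figures are in effect 0.929 - 0.05 and 0.769 - 0.05. No simulated trial went the other way.

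**The case against.** **Superiority by a margin is a legitimate hypothesis.** It is, and the written null is the stricter one, so applying it cannot inflate claims of benefit over zero. But 0.90 is then not its power, and no section re-powers the trial for it.

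**It may be a drafting slip.** This is plausible. The SAP's sentence can be read as naming the expected effect, and SAP 5.3 still speaks of open loop against closed loop. Still, the null and the alternative both carry the margin in symbols. If the analysts tested against zero, they departed from the approved text, and SAP 8 requires that to be logged.

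**The protocol contradicts the SAP.** A reader might infer this because Protocol 2 and 10.1 state no margin. The documents do not support it: Protocol 10 defers detail to the SAP, so silence there is not a conflict. The firm conflict is between the sample size sections and SAP 5.3.1.

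**The two tests give opposite verdicts.** This too is tempting, but showing a reduction greater than zero while not showing one greater than 3.125 points is a compatible pair of results. In practice the tests are nested. For the one-sided margin test to reject while the two-sided zero test does not, the SD of differences would have to exceed about 23 at n = 10 (3.125/(2.262 - 1.833) × √10) or about 16 at n = 7, against a planned 2.556.

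**The null was switched after the data were seen.** Nothing shows this. The SAP rests on protocol version "1.2 (dd 16-06-2022"), and its revision history describes D02 as adding only deviations and signatures, so the margin appears to date from D01 (29-08-2022). Silence in the deviation log is no evidence either way. The scripts might settle what was run ("For a list of the used scripts, functions, as well as the version numbers of the used libraries refer to the Data Analysis Plan"), but that plan is not among the documents and would not remove the conflict between SAP 3 and SAP 5.3.1.

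**Losing one sequence matters more.** Perhaps so: with only Humalog-Lyumjev participants left, treatment is confounded with period. That is a separate limit, and it qualifies every figure given here for n = 7.

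**Conclusion.** The point holds. The stated 0.90 does not belong to the primary test as written: at the planning effect, that test's power is its own significance level. That conclusion needs neither the SD, the correlation nor the sample size; only the level (5% or 2.5%) depends on the sides.

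The remaining sizes assume normal differences and the planning SD and correlation. The figures for n = 7 also assume no period effect, which cannot be checked with one sequence left. That the sizing used a two-sided test of zero is an inference from the match at n = 10, not something the documents state.

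A reader might go further and conclude that the trial had 5% power, or that its primary result is invalid. The documents do not support either, because they do not say which null was tested. If it was zero, power under the planning inputs was 0.77 two-sided at n = 7: below 0.90, but far from 5%.

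**What to change.** 1. State which null, which sides and which test (t or Wilcoxon) were used for the primary comparison, and when that was decided.
2. Report the mean paired difference with its 95% CI and the result against both 0 and -3.125. Do not promote the easier null after the data have been seen.
3. Then make one of two corrections.
   - *If zero was tested:* log it in SAP 8.1 as a departure from the null in 5.3.1, with the date and whether the decision came before or after data evaluation. Label it post hoc only in the latter case.
   - *If the margin was tested:* there is no deviation to log. Correct SAP 3 and note the same correction for Protocol 4.4, for example: *The 0.90 power applies to a test of zero difference. For the hypotheses in 5.3.1, power at a true reduction of 3.125 points equals the significance level of the test used ([sides], [test]); 90% power needs a true reduction of about [5.7 one-sided / 6.1 two-sided p-value] points with 10 subjects and [6.3 / 6.9] with 7 (t-test; SD 3.3, correlation 0.70).*
4. Either way, do not cite 0.90 for the 7-participant analysis, and let the confidence interval carry the interpretation.

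The cost is one or two text corrections and one extra reported comparison, with no new patients or data. The downside is that showing both results may leave a less clear-cut primary conclusion.
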